# Baseline and Other Summary Data

Sociodemographic characteristics, as well as information from the reproductive and contraceptive histories will be presented by gender. Other events, behaviours, and use details (use of lubricants, ease of insertion, etc.) associated with the use of the study condoms will be presented by condom type.

### VII. Risk Analysis

### Potential Risks

The study does not involve any procedures associated with significant risk. Couples at risk of pregnancy or at significant (high) risk of sexually transmitted infection are excluded from study participation. Minor side effects related to condom and lubricant use may include irritation, rash, itching, swelling and redness of the genitalia. These side effects are expected to be self-limiting.

#### Protection of Subjects

Detailed verbal and written instructions on correct condom use will be provided to all participants. Subjects will be instructed to contact research staff immediately if they encounter any problems related to the study or any major medical problem. Serious adverse events will be reported as soon as possible but no longer than 10 days to the sponsor and will be reported to the IRB in accordance with IRB requirements.

To assure subject confidentiality, subject names will not appear on study data forms. All data records will be identified by study ID number and may contain either initials or date of birth. Data records will not contain any other identifiers such as name, social security number, or address. Participants will be advised that any information they give will not be shared with their partner except at their specific request.

#### Potential Benefits

There are no direct benefits to subjects associated with study participation. The results of this study may benefit others in the future by making more contraceptive methods available.

#### Evaluation of Risks and Benefits

As discussed above, there are no known serious risks or substantial benefits associated with study participation.

# VIII. Description of Study Population

Monogamous couples protected against pregnancy by oral contraceptives, an IUD, contraceptive injections, contraceptive patch, or sterilization (tubal ligation or vasectomy) will be recruited via social media (Facebook), on-line advertising (Google), Internet classifieds (Craigslist, college newspapers), and from a database of previous study subjects to assure a diverse, representative study population. Couples will have had previous condom experience.

## IX. Description of Devices

The condoms used are described as follows:

	Test Condom I SAGCS-A	Test Condom 2 SAGCS-B	Control Natural Rubber Latex Male Condom* SAGCS-C
Commercial Name	Sagami Original 002 (24) ™	Sagami Original 001 (18) ™	Trojan Thintensity ™
Condom Type	Polyurethane	Polyurethane	Natural Latex
Nominal Length (mm)	190 +/-10	170 +/-10	195 +/-10
Nominal Flat width (mm)	58 +/-2	55 +/- 2	53 +/- 2
Nominal Thickness, mid-length (mm)	0.024 +/- 0.008	0.018mm +/- 0.008	0.055mm +/- 0.010
Lubricant type (cSt)	Silicone Oil 100	Silicone Oil 100	Silicone Oil 100
Lubricant quantity (g/pc)	0.40 - 0.60	0.40 - 0.60	0.40 - 0.60
Appearance	Cylindrical, with reservoir tip	Cylindrical, with reservoir tip	Cylindrical, with reservoir tip

\*Marketed, sold and distributed in the USA by Church & Dwight.

The test polyurethane and control natural rubber latex male condoms will be packaged in foiled tub packages. A label with the study identification number (protocol number) and condom identification number (A, B, or C), will be applied to each individual condom package. In addition,

in accordance with 21CFR812.5, labelling will also include the statement: "CAUTION: Investigational Device. Limited by Federal (or United States) Law to Investigational Use." Essential Access research staff will not know condom assignment until all study data have been analysed and tabulated.

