Sagami Rubber Industries, the manufacturer of the condoms, has been manufacturing condoms since 1934 and polyurethane condoms since 1990. Sagami polyurethane condoms are available in most countries throughout the world and the test condoms are currently marketed in Japan and throughout Asia demonstrating years of safe use of the product.

The primary objective of this study is to evaluate the breakage, slippage and acceptability of two test polyurethane male condoms of different thicknesses and size (0.024mm/58mm/190mm – SAGCS-A and 0.018mm/55mm/170mm – SAGCS-B) compared to a control commercial natural rubber latex male condom (Trojan Thintensity $^{\text{TM}}$  – 0.055mm/53mm/195mm - SAGCS-C). Acceptability will be evaluated by comparing physical attributes of the polyurethane and latex condoms, as well as perceptions about purchasing and using the products and condoms in general. The study will be conducted in accordance with ISO 29943-1:2017.

The Statistical Analysis Plan in Section VI. includes details of the methods of analysis that will be used. The primary effectiveness endpoint of the study is to confirm noninferiority with respect to total clinical failure rates (combined breakage and slippage) of two test polyurethane male condoms against a control latex condom. Each of the two test polyurethane male condoms will be compared independently against the control latex condom. A non-inferiority margin for the difference between the test condom total failure rate – the control natural rubber latex male condom total failure rate of 2.5% as specified in ISO 23409:2011 will be used to assess the results.

Test polyurethane condom SAGCS-A will be considered non-inferior to the control latex condom if a formal test of inferiority is rejected. Separately, test polyurethane condom SAGCS-B will be considered non-inferior to the control condom if a formal test of inferiority is rejected. Hence, one or both test condoms may be declared non-inferior based on the results of this three-arm functionality study. The study will be considered successful if either one or both of the test polyurethane condoms complies with the primary effectiveness endpoint.

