#### II. Protocol

# Summary

This investigation will enroll 300 heterosexual couples to use five test polyurethane male condoms SAGCS A (0.024mm/58mm/190mm), five test polyurethane male condoms SAGCS B (0.018mm/55mm/ 170mm), and five commercial control natural rubber latex male condoms SAGCS C (Trojan ThintensityTM- 0.055mm/53mm/195mm). Both test polyurethane condoms and the control natural rubber latex condom are lubricated with a silicone lubricant. Couples will be randomly assigned to the sequence of use of condom type. We estimate that this assignment pattern will yield over 1,000 evaluable uses out of 1,500 potential uses of each of the three study condom types. The study will compare the acceptability and functional performance (breakage and slippage) of the two test polyurethane condom types to that of the control natural rubber latex male condom through interviews and questionnaires with subjects. The study will be conducted in accordance with ISO 29943-1:2017.

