## Enrollment (E1)

If both partners are eligible after their screening, they will be invited to attend a Curbside exchange (E1) at which they will be enrolled into the study. This exchange will allow research personnel to meet the couple at a prearranged location (e.g. outdoor office space, clinic parking lot, etc.) that is safe for the participants and study staff to exchange study supplies and data. For subjects who are able to drive to the meeting site, subjects will stay in their car while research staff complete exchange procedures outside. Alternatively, research staff may meet the couple at their residence or other prearranged location and conduct the exchange at a sufficient distance (such as on their doorstep). If the exchange is conducted at a subject's residence, research staff must stay outside and not enter the home.

At enrollment (E1), both partners must be present with a valid, official government-issued photo identification to re-verify their identity before they can be enrolled and receive investigational product. The couple will receive their initial set of study supplies, including a penis measurement kit, five condoms of their first randomly assigned type of study condom, five condom reports, one

acceptability questionnaire for each partner and a supply of at least 4 oz. of Astroglide™ study lubricant to use if desired during their study participation. The couple will also receive five small sealable plastic pouches and one larger black plastic sealable plastic pouch for any condoms that break or tear. Each broken or torn condom should be sealed in an individual small pouch and the small pouch(es) should be placed inside the larger pouch. Any claimed broken or torn condoms should be returned double-bagged at the next Curbside exchange.

If a couple does not keep their scheduled enrollment, no further attempts will be made to contact the subjects.

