# Follow-Up (E2, E3, E4)

There will be three follow-up Curbside exchanges (E2, E3 and E4). Only one partner will be required to be present at each Curbside exchange.

E2 will be scheduled within three weeks of the enrollment. At E2, participants will return their completed condom reports and acceptability questionnaires. They will also return any unopened condoms and claimed broken or torn condoms. Used condoms should be returned double-bagged. Study staff may review reports and questionnaires for any missing or unclear responses. Simple clarifications that can maintain confidentiality and physical distance can be done Curbside. Further clarifications and follow-up will be completed remotely via telephone or video. Research staff will distribute five condoms of their next randomly assigned type of condom, five condom reports and one acceptability questionnaire for each partner. Additional lubricant will be supplied as needed at each exchange. The couple will also receive five small sealable plastic pouches and one larger black plastic sealable plastic pouch to double-bag any claimed broken or torn condoms. Each broken or torn condom should be sealed in an individual small pouch and the small pouch(es) should be placed inside the larger pouch. Any claimed broken or torn condoms should be returned double-bagged at the next exchange.

E3 will be scheduled within three weeks of the prior follow-up exchange. In addition to the procedures conducted during E2, a comparison form for each partner will also be distributed at E3.

E4 will be scheduled approximately three weeks after the prior follow-up exchange. At this exchange, participants will return their completed condom reports, acceptability questionnaires and comparison forms. They will also return any unopened condoms and claimed broken or torn condoms. Used condoms should be returned double-bagged. Study staff may review reports and questionnaires for any missing or unclear responses. Simple clarifications that can maintain confidentiality and physical distance can be done Curbside. Further clarifications and follow-up will be completed remotely via telephone or video.

If a couple does not keep their scheduled follow-up Curbside exchange, research personnel will initiate a reminder contact and reschedule the exchange.

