# V. Study Design

This study is a masked (investigators, research staff), three-arm crossover, randomized to sequence of use study designed to evaluate the functional performance (breakage, slippage) of two test polyurethane male condoms (.024mm/58mm/190mm – SAGCS-A, .018mm/55mm/170mm – SAGCS-B) each compared to a commercial natural latex condom. (.055mm/53mm/195mm - Trojan Thintensity $^{TM}$  – SAGCS-C). All three study condoms are lubricated with a silicone lubricant. Three hundred (300) couples will be enrolled and asked to use five condoms of each of the study condom type to yield a potential sample size of 1,500 uses for each type of lubricated condom. To minimize a potential learning effect, couples will be randomly assigned to one of six possible sequences of use of the study condoms:

- SAGCS-A SAGCS-B SAGCS-C
- SAGCS-A SAGCS-C SAGCS-B
- SAGCS-B SAGCS-A SAGCS-C
- SAGCS-B SAGCS-C SAGCS-A
- SAGCS-C SAGCS-A SAGCS-B
- SAGCS-C SAGCS-B SAGCS-A

From experience with previous condom breakage/slippage studies, we estimate that at least 85% of couples will complete all 15 condom uses to obtain an actual sample size of approximately 1,275 for each condom type.

The primary effectiveness endpoint of the study is to confirm noninferiority with respect to total clinical failure rates (combined breakage and slippage) of the two test male condoms independently against the control natural rubber latex male condom. As specified in ISO 23409:2011 a noninferiority margin,  $\delta$ , of 2.5% will be used.

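### Staff masking is claimed until analysis, but every package carries A, B or C, the letters the protocol ties to the products, and no concealed mapping or keyholder is described

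*Combined protocol and SAP*

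**What the plan says.** Section V (Study Design) states: "This study is a masked (investigators, research staff), three-arm crossover, randomized to sequence of use study". Section IX (Description of Devices) sets how long this lasts: "Essential Access research staff will not know condom assignment until all study data have been analysed and tabulated". Couples are not listed as masked.

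The same paragraph of section IX describes the label: a "condom identification number (A, B, or C), will be applied to each individual condom package". The table above it heads its columns SAGCS-A, SAGCS-B and SAGCS-C and gives commercial names. The Introduction describes "two test polyurethane male condoms of different thicknesses and size (0.024mm/58mm/190mm – SAGCS-A and 0.018mm/55mm/170mm – SAGCS-B", and the Summary in section II lists "five commercial control natural rubber latex male condoms SAGCS C". Section V writes the six randomised sequences in these letters.

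Staff handle the labelled product. At enrollment (E1) couples receive "five condoms of their first randomly assigned type of study condom"; at follow-up, "Research staff will distribute five condoms of their next randomly assigned type of condom". Unopened condoms come back to staff at the exchanges.

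Two other sections presume concealment. Section X allows the investigator to break a randomisation code in an acute medical situation. Section XIII has Los Angeles research staff randomise the product and send it, masked, to the Northern California office.

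Data Collection (section II) describes a comparison form on preferences between the two polyurethane types, whereas Acceptability measures (section VI) collects preference information for all three types.

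**The concern.** Staff masking is the only masking that this protocol claims. It is worth something here because staff touch the data after the couple has reported. They clarify missing or unclear responses at the exchanges and at exit, and they code and edit the records. If the package letter shows the product, that work is done by people who can know which uses are test and which are control. A final report that repeats the description in section V would then claim a safeguard that the procedures did not provide.

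The comparison form raises a related doubt. If it covers only the polyurethane types and tells couples which two sets to compare, the set left out is the control, whatever code is on the package.

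**Working it through.** This is mainly a comparison of texts; the arithmetic only counts extent.

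**1. Letters and products**

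| Letter | Product in the protocol | Where |
|---|---|---|
| A | polyurethane, 0.024 mm | Introduction; Summary; V; IX table |
| B | polyurethane, 0.018 mm | Introduction; Summary; V; IX table |
| C | commercial latex control | Introduction; Summary; V; IX table |

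The label in section IX uses A, B or C. No sentence says that the label letter is the SAGCS letter, and none says that it differs. With no second lettering in the document, the natural reading is that they are the same.

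**2. Extent.** The label goes on each package: 300 couples x 15 condoms = 4,500 packages, in 300 x 3 = 900 sets. On the natural reading all of them show the type.

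**3. Do sections X and XIII repair it?** A code that links a couple to a sequence does not hide a product whose letter is on the package. Only a scrambled link between letter and product would, and neither section describes one. Neither names a keyholder. Section XIII gives randomisation of the product to research staff, the group that section IX calls masked, and names no separate unmasked role.

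**4. Comparison form (conditional).** In the six sequences of section V the control is first in 2 (CAB, CBA), second in 2 (ACB, BCA) and third in 2 (ABC, BAC). A form that names only the two polyurethane sets by order of use therefore needs 3 versions, and each shows where the control lies. A form that covers all three sets needs 1 version and shows nothing. The form itself is not in the documents, so this holds only if it is as Data Collection describes and if it identifies the two sets.

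**5. Path to the primary endpoint.** A condom that slips off completely at withdrawal counts as a failure if it was held at the base, and is excluded if it was not (section VI, Observations contributing to the analyses, item 6). The answer on holding comes from the couple, but staff may clarify it when it is missing or unclear. To show the scale of one such item, take the planned 1,275 uses per type (85% of 1,500) and the plan's 4% failure rate, which gives 0.04 x 1,275 = 51 failures. Excluding one gives 50/1,274 = 3.92% instead of 4.00%, a shift of just under 0.08 percentage points against a margin of 2.5. This illustrates the path. It does not estimate bias: the documents do not say how many responses need clarification, or in which direction staff would err.

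**The case against.** The best answer is that a concealed mapping is presumed and merely left unwritten. Section XIII speaks of masked product, section X of a code that can be broken, and section IX puts the label and the promise of non-disclosure in one paragraph. It also calls the label a condom identification number, not a SAGCS code. If the letters are already scrambled, a sentence saying so and naming the keyholder would settle the label question. That stands as a possibility. It does not remove the point, because the text as written leads staff to the product.

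Second, the consequence is limited. Couples report breakage, slippage and holding themselves, the exclusions are fixed rules, and the primary analysis is prespecified. The condoms also differ in material and size, so couples may reveal the type in conversation whatever the label says. All of this stands, and it keeps the point to one of unsupported masking and avoidable risk.

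Third, the description of the comparison form may be a drafting slip, since Acceptability measures covers three types. That is fair. The two sections must be reconciled in either case, and the label conflict does not depend on the form.

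A reader might go further and infer that staff are certainly unmasked, or that the form certainly discloses the control. The documents support neither: the identity of the package letter and the SAGCS letter is a reading, and the form cannot be inspected.

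**Conclusion.** The point holds as a conflict between a stated design property and the procedures described to deliver it. It rests on one assumption, that the package letters are the SAGCS letters, which is the natural reading but is not stated outright. On that reading every package shows its type to the staff who dispense, collect, clarify and edit. The disclosure through the comparison form is secondary and conditional.

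A reader might infer that the non-inferiority result would be biased, or that the conclusion would change. The documents do not support that. Nothing in them lets the size or direction of any effect be estimated, and the outcome reports come from couples who are not claimed to be masked. What is shown is a masking claim that the plan does not support as written, and a risk of bias in clarification and editing that can be reduced cheaply. The plan should be changed before product is shipped.

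**What to change.** **Labels and key.** Before shipment, have the sponsor or another party outside the masked staff label packages with neutral codes unrelated to SAGCS-A, -B and -C. One undisclosed code per type is enough. Staff then randomise and dispense by code only, and forms and logs that identify condom type use the codes. Name the keyholder. A key held by the sponsor alone would not fit section X, under which the code may be broken before the sponsor is told; provide sealed or otherwise controlled access so that the emergency code break works as written. Bring sections V, IX, X and XIII into line.

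**Comparison form.** Reconcile Data Collection with Acceptability measures. If a comparison form is kept, have it cover all three sets by order of use and rank all three on each item. Full ranking matters: a question that asks only which was best loses the preference between the two polyurethane types whenever the control is chosen. That preference is extracted with the key at analysis.

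**If relabelling is not possible.** Drop the staff-masking claim, and do coding, editing and application of the section VI exclusions on records with condom type removed.

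**Cost.** New label text, a key list, protocol wording and a slightly longer form; no extra visits or couples. One version of the form serves all six sequences. Section IX says only that "The test polyurethane and control natural rubber latex male condoms will be packaged in foiled tub packages"; if those tubs do not look alike, overwrapping may be needed. The fallback costs wording and a data extract without condom type. Couples may still reveal the type, so masking is improved but not guaranteed.

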# X. Adverse Event Management

Subjects will be instructed to contact research staff immediately if they encounter any problems related to the study or any major medical problem. For this study, an Adverse Event (AE) Form is completed for any of the following: 1) genitourinary discomfort reported on a condom report that lasts more than an hour, 2) a non-genitourinary medical problem that might be related to condom use, 3) a new genitourinary condition that starts after use of a study condom, or 4) a serious adverse event. AE Forms are not completed for discomfort/problems that are reported on the condom report and last for less than an hour. A serious adverse event is defined as an adverse experience or concomitant illness that results in death, life-threatening situation, permanent disability, hospitalization, or congenital anomaly. An unanticipated event is defined as one that is not identified in nature, severity, or frequency in the protocol or human safety assessment.

The Principal Investigator (PI) will promptly notify the sponsor by telephone or email of any serious adverse event whether or not related to use of the study condom, or of any unanticipated event that is possibly related to use of the study condom. Also, the PI will notify the Essential Access IRB of any such event as required by IRB policies.

A clinical examination will be arranged for any subject who reports a persistent adverse reaction (irritation, rash, burning, etc.) which arises during his/her study participation if the adverse reaction has not resolved prior to the report. In an acute medical situation, the randomization code will be broken if the PI deems this essential for medical management of the subject. The PI will notify the sponsor as soon as possible, preferably before breaking the code. If the code is broken, the time and reason will be documented for study record and a copy sent to the sponsor.

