#### I. Introduction

Although latex condoms have long been available as contraceptive devices as well as a means for preventing the spread of sexually transmitted infections, they remain the only reversible method of contraception for men and an effective means of preventing STI's including the transmission of human immunodeficiency virus (HIV), which can progress to AIDS.

Polyurethane condoms are intended to prevent pregnancy, HIV/AIDS, and other sexually transmitted infections per the guidance document: Labeling for Natural Rubber Latex Condoms Classified Under 21 CFR 884.5300 - Class II Special Controls Guidance for Industry and FDA Staff. Although polyurethane condoms are outside the scope of this guidance document the general requirements for natural rubber latex condoms apply equally to polyurethane condoms.

Currently available non-latex condoms are not as widely known or used as latex condoms by many consumers who seek products for price, thinness, dependability, comfort, and attractiveness. Limitations of latex condoms include their ability to maintain performance while becoming thinner, sensitivity, as well as their potential to induce allergy. Up to 3% of the U.S. population may be unable to use latex products for this latter reason.

The development of non-latex condom options offering thinner properties while maintaining performance and protection from sexually transmitted infection (STI) and pregnancy constitutes a major contribution to public health. These new thinner polyurethane products are non-latex (non-protein) allergenic, capable of withstanding environmental extremes and with performance, sensation and aesthetic characteristics appealing to condom users

Non-latex condoms are the biggest single advancement in condom contraception and STI protection since condoms were first developed. Of importance is the nature of non-latex polyurethane condoms as they are latex allergy free and the material can be thinner, smoother, increase heat transfer, odorless, and have a natural appearance. Condoms made of polyurethane provide both burst and tensile properties that comfortably meet the natural rubber latex condom minimum standard requirements. Polyurethane condoms can help encourage condom use and thus reduce unwanted pregnancy and lessen the transmission of STI's. This study may therefore benefit millions of people.

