#### Data Collection

At the male and female phone screenings (SP-M and SP-F), an initial history will be obtained. The history will elicit information on previous condom use, sexual partners, coital patterns, history of STIs, vaginal infections, and disorders of the reproductive system.

At the first Curbside enrollment visit (E1), couples will be given a penis measurement kit and asked to take measurements of the male's erect penis (length and circumference) prior to use of the first study condom.

At every follow-up Curbside exchange (E2, E3, and E4), each couple will be asked to return a completed condom report for each use of a study condom within 30 minutes after ejaculation. These reports will elicit information on the conditions of use (who put on condom, use of lubrication, duration of vaginal intercourse, positions used during intercourse), subjective impression (ease of donning, fit, quality of lubrication), whether the condom was held at the base of the erect penis during withdrawal, and problems encountered (breakage, slippage, discomfort, lack of lubrication), circumstances of problems encountered (e.g. when noticed, duration). Written instructions and definitions/illustrations of potential condom problems such as breakage and slippage will be attached to the condom report forms.

After completing each set of five condoms, partners will complete acceptability questionnaires regarding their overall experience with each type of condom and return the questionnaires at the next follow-up Curbside exchange (E2, E3, and E4). These self-administered questionnaires, completed independently by both partners, will elicit perceived advantages, disadvantages, problems, and physical reactions related to condom use.

At the fourth and final Curbside exchange (E4), each partner will return a completed comparison form that elicits preferences between the two types of test polyurethane male condoms regarding sensation, comfort, lubrication, fit, ease of use, overall preference, etc.

Data coding, editing, and key entry will be performed at Essential Access Health. Entrypoint Plus software will be used to structure and maintain data files. Raw data from this study will be made available to the Sponsor as MS Excel files.

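### The under-one-hour bar on AE Forms is not limited to genitourinary discomfort, so a short, possibly related non-genitourinary problem on a condom report gets opposite instructions (minor)

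*Combined protocol and SAP*

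**What the plan says.** Section X requires an AE Form when any one of four triggers is met:

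1. discomfort in the genitourinary area, entered on a condom report and persisting beyond an hour;
2. a possibly related problem of another kind, which the plan words as "a non-genitourinary medical problem that might be related to condom use";
3. a genitourinary condition that is new since a study condom was used;
4. any event that meets the definition of serious.

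Only trigger 1 mentions a duration or the condom report; its wording is "genitourinary discomfort reported on a condom report that lasts more than an hour". The sentence after the list is the exclusion: "AE Forms are not completed for discomfort/problems that are reported on the condom report and last for less than an hour". It names neither trigger 1 nor genitourinary discomfort, and it makes no exception for the other triggers.

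The Data Collection part of Section II describes what the condom report collects for each use, including "problems encountered (breakage, slippage, discomfort, lack of lubrication), circumstances of problems encountered (e.g. when noticed, duration" and so on. It adds that each partner's acceptability questionnaire, completed after each set of five condoms, asks about physical reactions.

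In Section VI, the Acceptability measures text plans to report two things by condom type: genital discomforts, and adverse events judged probably or possibly related. It refers the reader to later text for the definitions of both. Section X is the later text that bears on this. It defines serious and unanticipated events, but for other adverse events it gives only the AE Form rule.

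**The concern.** Two rules in the same paragraph appear to give opposite instructions for one class of event. If site staff follow the exclusion as written, a short problem outside the genitourinary tract gets no AE Form even though trigger 2 asks for one. Because the by-condom-type safety summary takes its definitions from later text, and the form rule is the nearest thing there to a definition of a non-serious adverse event, the form rule may in practice decide what is counted.

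At stake is the completeness of a descriptive safety comparison between latex and polyurethane condoms, in which reactions away from the genital area are of some interest. Data are collected through two offices (Section XIII), so different readings of the paragraph could also be applied side by side.

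**Working it through.** The plan states no figure on this point and no arithmetic applies. The check is to cross event type with duration and with whether the event was entered on the condom report, and to read off what each rule requires.

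| Event | Under one hour, on condom report | Under one hour, not on condom report | Exactly one hour | Over one hour |
|---|---|---|---|---|
| Trigger 1 (by its terms, on the condom report) | No form; rules agree | Outside trigger 1 | Neither rule applies | Form |
| Trigger 2 | List: form. Exclusion: no form | Form | Form | Form |
| Trigger 3 | List: form. Exclusion: no form | Form | Form | Form |
| Trigger 4 | List: form. Exclusion: no form (see below) | Form | Form | Form |

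**Where the rules conflict.** The conflict is confined to one column: events under an hour that were entered on the condom report. For example, a possibly related skin reaction away from the genital area that clears in 40 minutes and is written on the report meets trigger 2 and also meets the exclusion. The same event told to staff by telephone, and not entered on the report, needs a form without any conflict.

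**Which triggers matter.** For trigger 4 the conflict is nominal, because Section X has a separate duty to notify the sponsor of serious events, with no duration limit. For trigger 3, a short genitourinary complaint may still appear under genital discomforts in the planned summary. Trigger 2 is where the practical consequence lies.

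**What is lost.** Every event in the conflict column is on the condom report by the exclusion's own terms. So the source record exists, and only the AE Form is in doubt. In the planned summary by condom type, a short genital discomfort has a reporting line that does not depend on the form. A short non-genital problem is not a genital discomfort. Without a form it may not be counted as an adverse event either, so it may appear in neither line.

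**The one-hour boundary.** Over an hour leads to a form and under an hour does not, which leaves exactly one hour unassigned. This touches trigger 1 only, since triggers 2 to 4 have no time limit. It is a missing detail and has no bearing on non-genital problems.

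**The case against.** The strongest reply is that the exclusion is simply the complement of trigger 1. Those are the only two places in the paragraph that mention the condom report and the one-hour threshold, and the SAP's separate line for genital discomforts fits that reading. It may well be what was intended. It is not what the text says, however: the exclusion drops the genitourinary qualifier and adds the word for problems, which is also the noun used in trigger 2. That word may instead echo the condom report's own list of problems, but staff should not have to decide which. What stands from this reply is that the scope is ambiguous and the contradiction holds on a literal reading only.

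A second reply is that other routes exist. Serious events, and unanticipated events possibly related to the condom, must be notified promptly whatever their duration. The side effects listed under Potential Risks in Section VII are all genital, so a short breathing reaction might well count as unanticipated, although the human safety assessment that also bears on this is not in the documents. Participants are told to contact staff about any problem, and the questionnaires ask about physical reactions. This stands as a strong mitigation. It does not settle tabulation, because nothing says that events arriving by these routes enter the by-condom-type summary without an AE Form.

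A third reply is that no safety hypothesis or between-arm safety test is planned. That is correct, and it limits the importance of the point.

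**Conclusion.** The point holds as a minor one. On a literal reading, a possibly related non-genitourinary problem under an hour that is entered on the condom report gets opposite instructions, and it may be missing from the related adverse events reported by condom type. This assumes that staff apply the exclusion as worded and that the summary is built from AE Forms; the documents do not state the second. The primary endpoint, sample size and power are unaffected. No event rate is given, so the size cannot be estimated.

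A reader might infer more than this, and the documents do not support it:

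- **That short reactions go unrecorded.** They are on the condom report by definition.
- **That the Introduction's figure gives a scale.** It says "Up to 3% of the U.S. population may be unable to use latex products for this latter reason", and 600 participants × 3% = 18. That is a general-population upper figure. The trial excludes self-reported latex or polyurethane allergy and recurrent adverse events with such products, and it requires previous condom experience. The figure is also not a rate of short, non-genital reactions entered on a condom report, so no share of control-arm events can be derived from it.
- **That allergy is the protocol's main safety contrast.** The Introduction lists it alongside thinness and sensitivity as a limitation of latex.
- **That the one-hour gap hides allergic reactions.** It affects genitourinary discomfort only.
- **That serious events could be suppressed.** Their notification route is separate and has no duration limit.

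**What to change.** Reconcile the two sentences in Section X in one of two ways:

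- limit the under-one-hour exclusion to the genitourinary discomfort of trigger 1 and say that it does not override triggers 2 to 4; or
- keep the exclusion as it is and state in Section VI that short non-genital problems taken from condom reports are tabulated by condom type together with the adverse events.

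In the same edit, assign exactly one hour to one side of trigger 1. Give both offices the same instruction.

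The cost is a wording change and, under the first option, a few more AE Forms. Under the second, the cost is an additional tabulation from data already collected.
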